# **10.4.** Safety Assessments

Safety monitoring will be performed throughout the study for all subjects. All AEs, regardless of causality or severity, will be recorded on the AE CRF. CAM2038 injections may be discontinued as clinically indicated.

#### 10.4.1. Adverse Events and Serious Adverse Events

The following definitions, developed in accordance with the United States (US) Code of Federal Regulations (CFR) and the International Conference on Harmonization (ICH) Clinical Safety

Version: 2.0, 17NOV2015 Page 57 of 99

Data Management Guidance for Industry, E2A, will be used for the purpose of identifying AEs in this clinical study.

An AE is any untoward medical occurrence in a subject administered a pharmaceutical product that does not necessarily have a causal relationship with this treatment. An AE can therefore be any unfavorable and unintended sign (e.g., including an abnormal laboratory finding), symptom, or increase in severity of a preexisting abnormality, temporally associated with the use of a medicinal (investigational) product, whether or not considered related to the medicinal (investigational) product.

## 10.4.1.1. Adverse Event Reporting

All AEs (except for withdrawal symptoms, see below) must be entered on the AE CRF, regardless of causality or severity. AEs include new AEs, worsening baseline conditions, clinically significant laboratory findings, disease-related signs and symptoms that were not present at baseline, and any events or findings that the Investigator feels are clinically significant. Withdrawal symptoms will be captured via specified assessments and should not be recorded as AEs.

Disease-related signs and symptoms that are present at baseline should not be recorded as AEs unless they worsen in severity or increase in frequency, but rather should be considered and recorded as pre-existing conditions.

Information collected concerning AEs will include the following:

- Name of the event
- Onset date
- Resolution date
- Severity (i.e., mild, moderate, or severe)
- Relationship to study drug
- Action and outcome
- Seriousness of event

All AEs will be documented and followed from the time the subject has signed the ICF until 14 days after the Follow-up Visit (or 30 days after Early Termination). Serious AEs and AEs that have been designated as possibly related to study drug will be followed until resolution or stabilization. At least 3 attempts will be made to contact the subject and after 3 unsuccessful attempts, a certified letter will be sent to the subject address that was provided to the site.

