Many studies have evaluated the conditions under which buprenorphine can be administered to opioid dependent individuals to avoid the precipitation of withdrawal. Collectively, these studies have shown that BPN-precipitated withdrawal is dependent on the following: 1) duration of action of the maintenance opioid (whereby precipitated withdrawal is more likely to occur in those maintained on long-acting opioids (e.g., methadone) than short-acting opioids (e.g., heroin), 2) the time since last opioid maintenance dose (whereby precipitated withdrawal is more likely to occur when opioid dosing is recent and more opioid is on board than when time for opioid wash-out has occurred and the individual is showing signs of opioid withdrawal, and 3) the absolute dose of BPN (whereby a higher BPN dose is more likely to precipitate withdrawal compared to a lower dose of BPN). The strategy proposed here addressed each of these principles in the following manner: 1) Subjects will be maintained on a short-acting opioid, morphine, rather than a long-acting opioid, 2) Morphine will be omitted for a period of ~12 hours and withdrawal signs and symptoms are expected to emerge during this interval prior to CAM2038 q1w administration (subjects will be required to score 8 points or greater on the COWS prior to being dosed with CAM2038 glw on Day 0 (Walsh et al., 2015), and 3) while the absolute depot dose of CAM2038 q1w at 24 and 32 mg is high, the more relevant factor is the initial concentration exposures following the injection and the rate of onset, whereby a slower rate of BPN delivery is associated with decreased likelihood of precipitated withdrawal (Rosado et al., 2007). The standard recommended approach (although not necessarily the most commonly used in clinical practice) is to begin dosing with 4 mg, wait for 2 hours and, in the absence of precipitated withdrawal, administer an additional 4 mg. A 4 mg sublingual tablet of BPN will produce a concentration of approximately 2 ng/mL (Cmax) at approximately 1 hour post-dose (Ciraulo et al., 2006), while an 8 mg initial dose would produce ~4.3 ng/mL (Cmax) at approximately 1.5 hour post-dose (HS-11-426). With respect to the CAM2038 q1w doses proposed for testing here, even at the highest dose (32 mg), BPN plasma levels will not exceed 2 ng/mL until approximately ~4 hours after administration. Thus, the initial BPN concentration exposure is predicted to be lower than the exposure typically seen during the first 2-4 hours of initial induction with SL products. Moreover, with CAM2038 q1w, concentrations will continue to slowly rise, reaching Cmax at approximately 24 hours post-dose. While BPN-precipitated withdrawal is a relatively rare occurrence in clinical practice, one strategy employed for treatment is to give more BPN. Given the pharmacokinetics of CAM2038 q1w, this potential approach for treating BPN-precipitated withdrawal is built into the product design and may serve to ameliorate any potential withdrawal effects. However, if withdrawal does occur, specific procedures have been included to ensure that subjects are assessed and receive treatment for symptoms (See Section 10.6).

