#### 10.6.2. Treating Opioid Withdrawal

If opioid withdrawal occurs after dosing with CAM2038 q1w (precipitated withdrawal), the following assessments will be collected every 4 hours while the subject is awake for at least 24 hours after dosing to include:

- 1) COWS,
- 2) OOWS,
- 3) VAS assessment of opioid withdrawal severity.

Treatment will be based upon clinical judgment of the medically responsible physician at each site. To ensure the safety of subjects, incidences of precipitated withdrawal in response to CAM2038 q1w will be followed carefully and an amendment of the protocol to ensure subjects are in a more advanced state of opioid withdrawal e.g., increase required COWS score from 8 to 12, to reduce the risk of BPN-related precipitated withdrawal, will be considered if more than one incidence occurs.

Ancillary medications that will be made available for symptomatic relief of all episodes of withdrawal (precipitated by CAM2038 q1w and other) are summarized in Table 5Error!

Reference source not found. Error! Reference source not found.

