9.2 SECONDARY EFFICACY OUTCOMES

In addition to the primary endpoint of change from baseline in E_{\max} of Drug Liking VAS, the following secondary endpoints will be calculated:

- High VAS E_{\max}
- Good Effects VAS E_{\max}
- Bad Effects VAS E_{\max}
- Sedated VAS E_{\max}
- Any Effects VAS E_{\max}
- Desire to use VAS E_{\max}

All these variables will be analyzed via the same methodology used to analyze the primary efficacy variable.

The follow secondary efficacy variables will be summarized by CAM2038 treatment group on the scheduled days that they are measured:

- Clinician-Rated Opioid Withdrawal Scale (COWS);
- Subjective Opioid Withdrawal Scale (SOWS);

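### The bar on recording withdrawal as an adverse event does not except withdrawal precipitated by CAM2038, so non-serious cases enter no AE table and no planned table gives their incidence by dose

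*Protocol*

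**What the plan says.** Protocol 10.4 gives the general rule: "All AEs, regardless of causality or severity, will be recorded on the AE CRF". Protocol 10.4.1.1 restates it with an exception: "All AEs (except for withdrawal symptoms, see below) must be entered on the AE CRF, regardless of causality or severity". It then closes the point: "Withdrawal symptoms will be captured via specified assessments and should not be recorded as AEs". Neither sentence separates withdrawal present before treatment from withdrawal brought on by the CAM2038 injection.

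Protocol 7.2 names the absolute buprenorphine dose as one determinant of precipitated withdrawal, "whereby a higher BPN dose is more likely to precipitate withdrawal compared to a lower dose of BPN". It also argues that slow release from the depot lowers the risk, and says that "BPN-precipitated withdrawal is a relatively rare occurrence in clinical practice". It gives no rate.

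Protocol 10.6.2 sets out the capture: "If opioid withdrawal occurs after dosing with CAM2038 q1w (precipitated withdrawal), the following assessments will be collected every 4 hours". Scoring is confined to waking time and runs for a minimum of one day from the injection. The instruments are COWS, OOWS and a withdrawal severity VAS. The same section says that a protocol amendment "will be considered if more than one incidence occurs".

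SAP 11.2 builds its AE tables from AE and SAE terms recorded on the case report forms. SAP 9.2 classes the withdrawal scales as secondary efficacy variables that "will be summarized by CAM2038 treatment group on the scheduled days that they are measured". In SAP Appendix A the withdrawal outputs are the COWS and OOWS change-from-baseline tables (series 14.2.10 and 14.2.11, Completer and ITT populations) and Listings 16.2.6.1 and 16.2.6.2.

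**The concern.** Excluding withdrawal from AE recording makes sense for subjects who arrive opioid dependent and are stabilised on morphine. Withdrawal precipitated by the study injection is different in kind: it is a reaction to the product under test. Safety and tolerability is a stated secondary objective, and the two randomised arms differ in exactly the factor, dose, that the protocol links to this reaction.

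If sites follow 10.4.1.1, a non-serious case gets no AE entry. It then lacks the investigator's AE grading of severity, relatedness, action and outcome, and it is missing from the AE rates for 24 mg and 32 mg. A reader of the study report could take its absence from those tables to mean that it did not occur.

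**Working it through.** The plan states no figure for this point, so there is none to reproduce. The check is mainly of text.

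**1. Does precipitated withdrawal meet the protocol's AE definition?** Protocol 10.4.1 covers any unfavourable sign or symptom associated in time with the product, whether or not related, and includes worsening of a pre-existing abnormality. Withdrawal that appears or worsens after the injection fits. Only the exclusion in 10.4.1.1 keeps it off the AE form.

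**2. Where would one non-serious episode after the Day 0 injection appear?**
- AE tables (series 14.3.2 to 14.3.9): nowhere, because they use recorded AE and SAE terms.
- COWS and OOWS change tables: partly. In Protocol Table 4 the Day 0 and Day 7 cells for both scales carry a footnote providing for assessment as needed if precipitated withdrawal occurs. SAP 9.2 summarises by scheduled day. Both scales are also given before hydromorphone on Days 1 and 8, about 24 hours after each injection.
- Population for those tables: Completer and ITT only. A subject who stops early because of the episode is absent from the Completer tables. Presence in the ITT tables depends on whether the as-needed scores count as post-baseline efficacy values.
- Withdrawal severity VAS: mentioned in the text of SAP 9.0, with no table in Appendix A.
- Listings: yes, for COWS and OOWS (16.2.6.1) and the VAS scales (16.2.6.2).
- Concomitant medication and disposition tables: the consequences may show, without a count of cases.

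Planned tables giving the number of subjects with precipitated withdrawal by CAM2038 dose: 0. Planned withdrawal tables in the Safety Population: 0.

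**3. Can the change-from-baseline means stand in for incidence?** If one subject of n = 24 has a COWS rise r above what it would otherwise have been, the group mean moves by r/n. With r assumed between 10 and 20 points (the documents give no value):
- r = 10: 10/24 = 0.42
- r = 20: 20/24 = 0.83

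A mean shift below one point would not reveal the case.

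**4. What would an incidence table show?** Rate = x/n, with exact (Clopper-Pearson) 95% limits. The lower limit is the 0.025 quantile of Beta(x, n−x+1), or 0 when x = 0. The upper limit is the 0.975 quantile of Beta(x+1, n−x). With n = 24 planned completers per dose:
- 0/24 = 0% (0 to 14.2)
- 1/24 = 4.2% (0.1 to 21.1)
- 2/24 = 8.3% (1.0 to 27.0)

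**5. How likely are at least two cases in the study?** P = 1 − (1−p)^48 − 48p(1−p)^47. The documents give no p, so these rates are assumed:
- p = 1%: 8%
- p = 2%: 25%
- p = 5%: 70%
- p = 10%: 96%

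Even at low rates, a handful of cases is a realistic outcome that the report should be able to state by dose.

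**6. Day 21.** Protocol 7.1.5 says that the follow-up call should ask about withdrawal effects. Table 4 schedules no withdrawal scale that day, and 10.4.1.1 bars an AE entry, so what the subject reports has no named place. Treatment emergence is also unsettled. Protocol 12.3.4.1 ends non-serious TEAEs at discharge. SAP 11.2 tabulates events up to 30 days after the last dose, and Day 21 is 21 − 7 = 14 days after the second CAM2038 injection.

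**The case against.** The best defence is that the exclusion is deliberate. Section 10.4.1.1 is an express exception to a general rule, and it sends withdrawal to dedicated scales. Subjects must already be in mild withdrawal (COWS of at least 8) to receive the Day 0 injection, so AE entries would mix background with precipitated withdrawal. The event is called rare, no formal safety comparison is planned, and the primary endpoint is untouched. All of that stands, and it is why the exclusion for background withdrawal should stay. It does not explain why a drug reaction that the protocol names has no incidence reported by dose.

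Four stronger readings are tempting, and the documents do not support them:
- **That post-injection episodes reach only listings.** The Table 4 footnote on the Day 0 and Day 7 cells, the summary by scheduled day and the Day 1 and Day 8 scores mean that some of the data enter the COWS and OOWS tables.
- **That the count behind the amendment provision has no record.** Section 10.6.2 requires assessments every 4 hours, and the severity VAS is given only when precipitated withdrawal occurs, so its presence marks a case. The provision is also operational and is not tied to end-of-study tables. What is missing is a case definition, with a score or time window.
- **That cases would show as 0% in every AE table.** Protocol 10.4.1.2.1 puts all SAEs on the AE form, so a serious case can reach Table 14.3.7. The protocol does not say whether the withdrawal exclusion overrides this.
- **That withdrawal at Day 21 is the same problem.** It would follow the decline of the depot and is not precipitated by the injection. It is a separate gap in recording.

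**Conclusion.** The point holds as a reporting gap that should be closed. The data are collected and listed. What the plan lacks is an AE record for non-serious precipitated withdrawal and any table of affected subjects by CAM2038 dose. Each such case is about 4.2% of an arm that the AE rates would omit, and group mean changes would hide it.

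This rests on sites following 10.4.1.1 as written. The 4.2% uses 24 planned completers per dose. The Safety Population may be larger because of over-enrolment and replacement, which would make each case a somewhat smaller share. The COWS rise and the event rates are assumptions. Sample size, power, type I error and the primary analysis are not affected.

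**What to change.** 1. Reconcile Protocol 10.4 with 10.4.1.1. Keep the exclusion for background withdrawal, and record withdrawal that the investigator judges precipitated by CAM2038 as an AE with severity, relatedness and outcome. The sponsor should set the case definition. State that the exclusion does not override SAE recording.
2. Add one SAP table in the Safety Population: number and percentage of subjects with precipitated withdrawal by CAM2038 dose and by injection (Day 0, Day 7), with peak COWS.
3. Separately, state where withdrawal effects reported at the Day 21 call are recorded, and align the two TEAE windows so that their status is clear.
4. While editing SAP 9.2, correct the scale name. It lists SOWS, whereas the Protocol and Appendix A use OOWS.

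The cost is one clause, one case definition, one descriptive table from data already collected, and minor wording. The downside is a somewhat higher reported AE rate.

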#### 10.4.1.2. Serious Adverse Event

A SAE or reaction is any adverse drug experience occurring at any dose that results in any of the following outcomes:

- Death
- Is life-threatening (at the time of the event)
- Requires inpatient hospitalization or prolongation of existing hospitalization,

Version: 2.0, 17NOV2015 Page 58 of 99

- Results in persistent or significant disability/incapacity
- Is a congenital anomaly/birth defect (in an offspring)
- An Important medical event that may not result in death, be life-threatening, or require hospitalization may be considered an SAE when, based upon appropriate medical judgment, the event may jeopardize the subject and/or may require medical or surgical intervention to prevent one of the outcomes listed in this definition.

All AEs requiring hospitalization or prolongation of a pre-existing hospitalization should be reported as SAEs unless they occur greater than 14 days after the Follow-up phone call (or 30 days after Early Termination) AND are not considered to be drug-related by the Investigator.

Hospitalizations meeting the following criteria will not be reported as an SAE but must be recorded on the appropriate CRF: study specified hospitalization, short-term administrative hospitalization for procedures, tests or treatments of conditions that would not otherwise constitute an SAE, elective hospitalizations.

## 10.4.1.2.1. Serious Adverse Event Reporting

Serious AEs must be reported to the Sponsor or designee within 24 hours of knowledge of the event. All SAEs that occur while a subject is receiving study drug and within 14 days following the Follow-up phone call (or 30 days after Early Termination) are reportable within 24 hours. During the follow-up period beyond 14 days from Follow-up (or 30 days after Early Termination), only those SAEs that are considered to be possibly related to study drug should be reported within 24 hours.

The procedure for reporting a SAE is as follows:

- Within 24 hours of knowledge of the event, the site must contact the Sponsor (or designee) by telephone or facsimile to report the event.
- The initial report should include all information known at the time of the report (additional information can be reported as discovered). Do not delay the initial reporting in order to obtain resolution or follow-up information.
- The site will complete the provided SAE report form that includes the following information, as available:
  - Subject ID
  - o Basic demographic information (age, gender, weight)
  - Outcomes attributed to the event (death, life-threatening hospitalization [new or prolonged], disability, congenital anomaly, required medical intervention to prevent permanent impairment/damage, etc.)
  - Onset date and severity of the event
  - Brief description of the event including frequency and severity of symptoms leading to diagnosis
  - List of relevant test results and laboratory data
  - Any other relevant history

Version: 2.0, 17NOV2015 Page 59 of 99

- Whether the study drug was discontinued
- Whether the assigned treatment oral or injectable therapy was discontinued and/or dose titration discontinued, as applicable
- o Investigator's assessment of causality
- Other concomitant medication and medical history

The SAE report form should then be emailed to the Sponsor (or designee) or faxed per instructions in the SAE Reporting and Management Plan.

The Medical Monitor or another representative of the Sponsor may contact the Investigator to request additional information regarding the event or to confirm information. All SAEs will be entered on the AE CRF. The same nomenclature should be used on both the SAE report and the AE CRF.

Specific instructions for SAE reporting and a copy of an SAE report form are provided in the MOP.

The Investigator is responsible for the complete and timely reporting of all SAEs to the Sponsor (or designee), reporting pertinent follow-up information on the SAE, and notifying the appropriate IRB/Independent Ethics Committee (IEC) of the occurrence of and details surrounding the event. In the event there is a question as to whether the AE is serious, the event should be reported.

#### 10.4.2. Pregnancy

Pregnancies among trial subjects should be reported to the Sponsor or designee as soon as possible after learning of the event. Subjects who become pregnant will be withdrawn from the study and be referred back to the care of their usual provider or continue in the study after discussion with and documentation by the Principal Investigator or his/her designee. Pregnancies will be recorded as an AE in the eCRFs. Follow-up information will be obtained where possible (with the consent of the subject or their partner) regarding the course and outcome of the pregnancy, including any post-natal sequelae in the infant.

#### 10.4.3. Clinical Laboratory Assessments

All protocol-specified laboratory tests on blood and urine samples will be performed by each CRU's local laboratory. The local laboratory will generate laboratory reports and forward them to the clinical site in a timely manner. It is the responsibility of the local medically responsible investigator to review and sign all lab reports expeditiously, in order to document appropriate safety monitoring of study subjects. The Investigator should sign and date each lab report concurrent with her or his review, and should indicate the clinical significance of each abnormal/flagged value by noting "NCS" (not clinically significant) or "CS" (clinically significant), for example. Notations indicating that a value is clinically significant should also include a brief description of the underlying disease or condition that is associated with the value, e.g., "CS/mild anemia." In general, abnormal, clinically significant laboratory values are expected to be associated with an item recorded in medical history or with an AE.

Version: 2.0, 17NOV2015 Page 60 of 99

**Table 7** Clinical Laboratory Assessments

Hematology	Biochemistry	Urinalysis
Hematocrit Hemoglobin Red blood cell (RBC) count RBC Morphology Mean corpuscular volume Mean corpuscular hemoglobin Mean corpuscular hemoglobin concentration Total and differential (absolute) white blood cell count Platelets  Coagulation  Prothrombin time (PT), International normalized ratio (INR)	Sodium Potassium Magnesium Calcium Glucose (random) Bicarbonate Chloride Creatinine Total protein Blood urea nitrogen Albumin Total bilirubin Alanine transferase Aspartate transferase Lactic dehydrogenase Amylase Lipase Gamma-glutamyl transferase Alkaline phosphatase Creatine phosphokinase Total cholesterol (non-fasting) FSH	Dipstick illicit drug screen including buprenorphine, barbiturates, benzodiazepines or methadone Color pH Specific gravity Ketones Protein Glucose Bilirubin Nitrite Urobilinogen Occult blood Microscopic examination of sediment, only if urinalysis dipstick results are abnormal
Serology testing (optional)		
HIV-1 and HIV-2 Hepatitis B surface antigen Hepatitis C Antibody (HCVAb)		

Blood and urine samples will be collected, processed, and shipped according to instructions from the local laboratory. Additional laboratory samples may be taken at the discretion of the Investigator if the results of any tests fall outside reference ranges or clinical symptoms necessitate testing to ensure safety. Blood volumes required per draw, laboratory test will be determined by each site's local laboratory. Specific hematology, coagulation, biochemistry, and urinalysis assessments are listed in Table 7. It is up to the investigator to review lab results and determine if the abnormal lab results are clinically significant.

Version: 2.0, 17NOV2015 Page 61 of 99

In addition to the clinical laboratory tests, pregnancy testing for the presence of  $\beta$ -human chorionic gonadotropin in serum will be performed at the visits defined in Table 4. Results of serum pregnancy tests will be reported and determined to be negative prior to study continuation and/or dosing. Urine pregnancy testing will be performed prior to the Qualification Phase challenge. As an additional precaution, urine pregnancy tests will be administered weekly (on Day 0 and Day 7) prior to CAM2038 q1w dosing.

